## 6.6. ANALYSIS OF CI ENDPOINTS

Evaluation Variable / Question	Level of Measurement	Analysis Plan					
Endpoints – Primary Endpoint							
Use variable Total ASES Score 24 Months [points]:							
Based on the underlying distribution of the data and the result of the normality assessment, either the parametric one-sample t-test or the non-parametric one-sample sign test will be used to compare the 24 months postoperative ASES Shoulder Score results of the ReUnion RSA group against the lower maximum acceptable difference ( $-\theta$ ) of 51.87 points.							
The analysis of the primary endpoint will be part of the final report.							

Table 6.6.1: Endpoints – Primary Endpoint Tables List

Evaluation Variable / Question	Level of Measurement	Recode and Analysis Plan	Inclusion		
Adverse Events – Time to (earliest) Device-Related Adverse Event / Incident			IR	FR	N/A
Creation of variable Difference between Date of Surgery [dd.mm.yyyy] and Date of First Device Related Adverse Event [dd.mm.yyyy] in [ ] days [ ] (Variable(s): VISITDT; AEONSTD)	Quantitative, ratio	Case summary with number and percentage of valid cases/values, missing cases/values (if any) and total cases/values. Mean, median, interquartile range, maximum, minimum, standard deviation, 95% confidence interval for mean, Shapiro-Wilk Test.		X	
Creation of variable Difference between Date of Surgery [dd.mm.yyyy] and Date of “most recent” Visit [dd.mm.yyyy] in [ ] days [ ] (Variable(s): VISITDT)	Quantitative, ratio	N/A (Analyzed above), used for survivorship		X	
Create new variable “Grouping variable – First Device Related Adverse Event” (Variable(s): AEONSTD)	Qualitative, nominal	- censored = survivors - events = first (earliest) Device Related Adverse Event		X	

Create new variable “Combined Time – First Device Related Adverse Event” (Variable(s): AEONSTDT)	Quantitative, ratio	- Use time between surgery and “most recent” visit for surviving subjects - Use time between surgery and first device related adverse event for subjects with device related adverse event	X	
Use variables “Combined Time – First Device Related Adverse Event” and “Grouping variable – First Device Related Adverse Event”	Qualitative, nominal Quantitative, ratio	Case summary with number and percentage of valid cases/values, missing cases/values (if any) and total cases/values. Kaplan-Meier survival analysis: subject ID, time, status, cumulative proportion, Kaplan-Meier estimate, standard error of KM estimate, number of cumulative events, number of remaining cases, mean for survival time with 95% confidence interval, survival graph, hazard graph.	X	

Table 6.6.2: Endpoints – Secondary Endpoint Time to (earliest) Device Related Adverse Event / Incident Tables List

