11.3.3. Secondary Endpoints

The incidence of device-related AEs and implant survivorship will be assessed up to 10 years after the index procedure and monitored through collection and analyses. These analyses will be part of the annual and final reports.

Furthermore, time to (earliest) device-related AEs will be analyzed as well. For analysis of the time to the (earliest) device-related AEs as well as the time to secondary procedure (revision, removal, reoperation), the Kaplan-Meier method will be used. The time between surgery and the last available assessment will be used together with the time between date of surgery and the date of secondary procedure. Considered variables, the level of measurement and the planned analysis steps are listed in detail in the SAP.

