13.3. RELATIONSHIP TO THE DEVICE

Only events considered possibly, probably or definitely related to the device will be captured for this clinical investigation.

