13.5. FORESEEABLE ADEs, SADEs and INCIDENTS

ADEs, SADEs and incidents which may be expected as part of the surgical intervention include:

- *Perioperative complications*
 - Malpositioning of the humeral or glenoidal component
 - Oversizing of implant components
 - Undersizing of implant components
 - Intraoperative fracture of the humerus or glenoid
 - Humeral cement leakage, if applicable
 - Nerve injury, mild (minor motor or sensory loss, or spontaneous recovery)
 - Nerve injury, severe (significant motor or sensory loss or requiring surgical revision)
 - Vessel injury
 - Tendon injury
 - Wound complications (e.g. hematoma, wound healing disturbances)
 - Superficial infection
 - Deep infection
 - Deep vein thrombosis
 - Pulmonary embolism
- *Complications in the follow-up period*
 - Implant dislocation
 - Other subluxation or instability, symptomatic
 - Implant component dissociation, humeral cup from humeral stem
 - Implant component dissociation, humeral insert from humeral cup
 - Implant component dissociation, glenosphere from baseplate
 - Implant fretting or crevice corrosion
 - Implant breakage/wear, humeral or glenoidal
 - Implant loosening, humeral
 - Implant loosening, glenoidal with or without screw breakage
 - Radiographic lucency, humeral or glenoidal
 - Pain related to the implant, severe
 - Late infection (e.g. hematogenous or protracted)

- Periprosthetic fracture of the humerus or glenoid
- Stress fracture of the acromion or the scapular neck
- Stress fracture of the coracoid
- Scapular notching, asymptomatic or symptomatic
- Stiffness
- Heterotopic ossification, asymptomatic or symptomatic
- Healing disturbances of subscapularis tenotomy, if applicable
- Non-union of lesser tuberosity osteotomy, if applicable
- Malunion of lesser tuberosity osteotomy, if applicable

14. Reoperations

Reoperations and reason(s) for reoperations will be collected throughout the course of the clinical investigation. A reoperation may include but not limited to irrigation and debridement, revision surgery and/or implant removal.

15. Ethics

This clinical investigation is to be conducted according to International Conference of Harmonisation of Good Clinical Practice (ICH-GCP), applicable regulations, institutional research policies and procedures, Declaration of Helsinki and in compliance with the CIP. Investigators will be trained on the clinical investigation devices and surgical techniques prior to implanting clinical investigation subjects.

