#### 6.1. HARMS AND SAFETY

Categorization and definitions of (Serious-, Unanticipated-) Adverse Device Effects, (Serious-) Incidents are given in the CIP.

Evaluation Variable / Question	Level of Measurement	Analysis Plan	Inclusion		
			IR	FR	N/A
Adverse Events / Incidents					
Perioperative/Postoperative AE (Variable(s): PERPOST)	Qualitative, nominal	Proportions, frequencies, column and row totals, missing proportion (if any).	X	X	
Device-Related Adverse Event / Incident (Variable(s): AEEVENT; AEOTHER)	Qualitative, nominal	Proportions, frequencies, column and row totals, missing proportion (if any). Listing of other Events/Incidents.	X	X	
Describe the AE/Incident (Variable(s): AEDESCRP)	Qualitative, nominal	Listing of other Events/Incidents Description.			X
Unanticipated Adverse Device Event? (Variable(s): AEUADE)	Qualitative, nominal	Proportions, frequencies, column and row totals, missing proportion (if any).	X	X	
Severity (Variable(s): AESEVER)	Qualitative, nominal	Proportions, frequencies, column and row totals, missing proportion (if any).	X	X	
Action Taken (Variable(s): ACTNONE; ACTMEDS; ACTSURG; ACTSHORT; ACTPROHS; ACTOTHER; ACTOTHSP)	Qualitative, nominal	Proportions, frequencies, column and row totals, missing proportion (if any). Listing of given Other specifications.			X
AE Resolution (Variable(s): AERESOLV)	Qualitative, nominal	Proportions, frequencies, column and row totals, missing proportion (if any).			X
Outcome (Variable(s): AEONWOTR; AEONWTTR; AEREWOTR; AEREWTTR; AEATEDISB; AEPERMD; AESUEXP)	Qualitative, nominal	Proportions, frequencies, column and row totals, missing proportion (if any).			X
Creation of variable Number of Adverse Device Effects by Site (Variable(s): AEEVENT; SITENUM)	Qualitative, nominal	Proportions, frequencies, column and row totals, missing proportion (if any).	X	X	

Creation of variable Number of Adverse Device Effects per Subject and Site (Variable(s): AEEVENT; SITENUM; SUBID)	Qualitative, nominal	Proportions, frequencies, column and row totals, missing proportion (if any).	X	X	
---	----------------------	---	---	---	--

Table 6.1.1: Adverse Events / Incidents Tables List

Evaluation Variable / Question	Level of Measurement	Analysis Plan	Inclusion		
			IR	FR	N/A
Reoperation					

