### 6.7.3. Reoperation Surgery

For analysis of the time to the reoperation, the Kaplan-Meier method will be used. The times between surgery and the most recent or last available assessment per subject will be used

together with the times between surgery and the date of reoperation (earliest reoperation in case that one subject experienced more than one reoperation). This analysis is part of the final report.

Evaluation Variable / Question	Level of Measurement	Recode and Analysis Plan
Adverse Events / Reoperation Surgery		
Creation of variable Difference between Date of Surgery [dd.mm.yyyy] and Date of First Reoperation [dd.mm.yyyy] in [ ] days [ ] (Variable(s): VISITDT)	Quantitative, ratio	Case summary with number and percentage of valid cases/values, missing cases/values (if any) and total cases/values. Mean, median, interquartile range, maximum, minimum, standard deviation, 95% confidence interval for mean, Shapiro-Wilk Test.
Creation of variable Difference between Date of Surgery [dd.mm.yyyy] and Date of “most recent” Visit [dd.mm.yyyy] in [ ] days [ ] (Variable(s): VISITDT)	Quantitative, ratio	N/A (Analyzed above), used for survivorship
Create new variable “Grouping variable – First Reoperation” (Variable(s): VISITDT)	Qualitative, nominal	- censored = survivors - events = first (earliest) Reoperation
Create new variable “Combined Time – First Reoperation” (Variable(s): VISITDT)	Quantitative, ratio	- Use time between surgery and most recent visit for surviving subjects - Use time between surgery and first reoperation for subjects with reoperation(s)
Use variables “Combined Time – First Reoperation” and “Grouping variable – First Reoperation”	Qualitative, nominal Quantitative, ratio	Case summary with number and percentage of valid cases/values, missing cases/values (if any) and total cases/values. Kaplan-Meier survival analysis: subject ID, time, status, cumulative proportion, Kaplan-Meier estimate, standard error of KM estimate, number of cumulative events, number of remaining cases, mean for survival time with 95% confidence interval, survival graph, hazard graph.

Table 6.7.3.1: All Assessments – Reoperation Surgery Tables List

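### The only time-to-adverse-event analysis stops at the first device-related event of any kind, so no planned analysis gives the cumulative incidence of follow-up implant complications

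*SAP*

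**What the plan says.** Protocol 8.2 and 11.3.3 name the incidence of device-related adverse events as the secondary safety endpoint, assessed to 10 years. Protocol 11.3.3 adds a time-to-earliest-event analysis. SAP 6.6, Table 6.6.2 implements it. The status variable is "events = first (earliest) Device Related Adverse Event", everyone else is censored, and the time rule is "Use time between surgery and first device related adverse event for subjects with device related adverse event".

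What can count as an event is set in the protocol:

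- Section 13.3: "Only events considered possibly, probably or definitely related to the device will be captured for this clinical investigation".
- Section 13.5, perioperative list: sizing errors, intraoperative fracture and mild nerve injury, among others, and "Wound complications (e.g. hematoma, wound healing disturbances".
- Section 13.5, follow-up list: dislocation, dissociation, late infection and "Implant loosening, glenoidal with or without screw breakage", alongside notching and heterotopic ossification without symptoms, and radiographic lucency.

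Two further time-to-event safety analyses are planned. Protocol 11.3.3 says that for "time to secondary procedure (revision, removal, reoperation), the Kaplan-Meier method will be used", and SAP 6.7.3 implements this with "events = first (earliest) Reoperation". SAP 6.7.2 covers death. Table 6.1.1 tabulates event type, severity, number of effects per subject and "Perioperative/Postoperative AE (Variable(s): PERPOST", all as frequencies.

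**The concern.** The follow-up runs to 10 years, and much of what Protocol 13.5 lists for that period is failure of the implant or its fixation. A single curve that ends at the earliest event of any kind mixes these with events of the operation itself and with incidental radiographic findings. A subject with a device-related hematoma in the first week counts as an event then. If the glenoid component loosens in year 6, the curve does not register it.

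The perioperative-to-postoperative boundary is only part of the problem. Symptom-free notching recorded at 12 months pre-empts a later dislocation in the same way. Splitting the curve by period alone would therefore not be enough.

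At stake is whether the study can state, with time at risk accounted for, what proportion of implanted subjects have had a dislocation, dissociation, loosening, breakage, late infection or periprosthetic fracture by a given year.

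**Working it through.** The plan states no adverse-event rate, so there is no figure to reproduce. The check has two parts.

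**1. Where a later implant complication appears after an earlier minor event**

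- Table 6.6.2 curve: not at all, because the subject's time ended at the first event.
- Table 6.1.1: counted by type and severity, as proportions without time at risk.
- Table 6.1.2: counted as a reason for reoperation, if there was one, again as a frequency.
- Table 6.5.4: counted if seen on a radiograph, separately at each visit. This is a finding per visit, not a cumulative incidence. Protocol 10.4 leaves imaging to each institution's standard of care and asks for no extra X-rays.
- SAP 6.7.3 curve: counted only if it leads to surgery and no reoperation came before. Protocol 14 pools debridement with revision and removal, so an early washout pre-empts a later revision here too.

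The crude tables are a weak substitute because of expected losses. Both documents assume 56% overall drop-out. With 80 enrolled, 80 × 0.56 = 44.8, so about 45 leave and about 35 remain. A crude proportion over 80 treats the 45 as event-free after they left.

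**2. Size of the omission within the Table 6.6.2 curve**

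Assumptions, none from the documents: a proportion p of subjects has an early minor device-related event; the risk of a later major complication is RR times as high in them as in the others; follow-up is complete. The share of subjects with a later complication who do not contribute it is

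share = p·RR / (p·RR + 1 − p).

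For scale, take a later complication in 10% of 80 subjects, that is 8.

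| p | RR = 1 | Omitted of 8 | RR = 2 | Omitted of 8 |
|---|---|---|---|---|
| 5% | 5% | 0.4 | 0.10/1.05 = 9.5% | 0.8 |
| 10% | 10% | 0.8 | 0.20/1.10 = 18.2% | 1.5 |
| 20% | 20% | 1.6 | 0.40/1.20 = 33.3% | 2.7 |
| 30% | 30% | 2.4 | 0.60/1.30 = 46.2% | 3.7 |

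Take the row p = 20%, RR = 2. The later risk in subjects without an early event is 0.10/(0.8 + 0.2 × 2) = 0.083. The curve reaches 0.20 + 0.80 × 0.083 = 26.7% with any first event. The true figure for the later complication is 10%, and nothing in the output lets a reader separate the two. Restricting attention to subjects still at risk after the early period gives 8.3%. That matches the true 10% only if RR = 1, and only if no incidental finding came first.

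**The case against.** The curve does what it claims. The protocol prespecifies time to the earliest device-related event, the safety endpoint pools intraoperative and postoperative events, and Table 6.6.2 is labelled accordingly. No section says that it estimates late failure. Subjects with an early event are not excluded; they are counted as events. All of this stands, and it is why the curve should be kept.

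A reader might infer that this is the plan's only time-to-event safety analysis, or that later failures are hidden. The documents support neither. Reoperation and death have their own Kaplan-Meier analyses. Tables 6.1.1, 6.1.2 and 6.5.4 report later events by type, and SAP 4.6 shows missing cases at each postoperative assessment. What is missing is an estimate that accounts for time at risk.

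It might also be inferred that perioperative events are always trivial, or that subjects who have them are at higher later risk. The perioperative list also contains deep infection, severe nerve injury and pulmonary embolism, and the documents are silent on later risk. Protocol 13.3 limits capture to events at least possibly related to the device, so not every hematoma would count.

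Finally, separate curves for each failure type in 80 subjects, about 35 of them after the assumed drop-out, would be too sparse to be useful. That objection is sound and limits the remedy.

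**Conclusion.** The point holds in this form: the only time-to-adverse-event analysis ends each subject at the first device-related event of any kind. A minor perioperative event or an asymptomatic finding therefore removes a later implant complication in that subject from the curve. The other outputs show such complications as crude frequencies, or as a first reoperation if surgery follows. None gives the cumulative incidence of follow-up implant complications.

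The structural finding rests on the documents alone. Its size does not. The range of about 5% to 46% depends on assumed early-event rates of 5% to 30%, a risk ratio of 1 to 2 and complete follow-up. With 8 later complications among 80 subjects, that is about 0.4 to 3.7 subjects. It concerns a secondary safety analysis and leaves the primary ASES comparison untouched. The change is worth making because late complications will probably be few and the data are already planned.

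**What to change.** In SAP 6.6:

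- Keep the any-event curve of Table 6.6.2, labelled as time to first device-related event of any kind.
- Report perioperative device-related events as a proportion of implanted subjects, using PERPOST.
- Add one analysis of time to first follow-up implant complication. The event is a composite fixed in advance from Protocol 13.5: dislocation, component dissociation, loosening, breakage, late infection or periprosthetic fracture. Every implanted subject is at risk from surgery regardless of earlier adverse events. Death is a competing event, so the estimate is a cumulative incidence with a 95% confidence interval and numbers at risk by year.
- Report the individual failure types descriptively, without separate curves.

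The inputs are already named in the SAP: the event type (AEEVENT), PERPOST, the event onset date and the date of death. Only the variable names and labels are visible, so the eCRF code lists should be checked to confirm that AEEVENT identifies each component of the composite and that PERPOST follows the division in Protocol 13.5.

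The cost is SAP wording, one status variable and one time variable. No new data are collected. The downside is one more output with few events and a wide interval, which the report should say.

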## 6.7. ADDITIONAL ANALYSIS

### 6.7.1. ASES Comparison

The comparison of the ASES Shoulder Score must compare all Total ASES Shoulder Scores of all follow-up visits against each other (m x n) in accordance to table 6.7.1.1 and the analysis tables listed in this chapter. This analysis is part of the final report only.

Comparison		Follow-up Visits (n)												
		Preop	6 Weeks	6 Months	12 Months	24 Months	36 Months	48 Months	60 Months	72 Months	84 Months	96 Months	108 Months	120 Months
Follow-up Visits B (m)	Preop	x												
	6 Weeks	x												
	6 Months	x	x											
	12 Months	x	x	x										
	24 Months	x	x	x	x									
	36 Months	x	x	x	x	x								
	48 Months	x	x	x	x	x	x							
	60 Months	x	x	x	x	x	x	x						
	72 Months	x	x	x	x	x	x	x	x					
	84 Months	x	x	x	x	x	x	x	x	x				
	96 Months	x	x	x	x	x	x	x	x	x	x			
	108 Months	x	x	x	x	x	x	x	x	x	x	x		
	120 Months	x	x	x	x	x	x	x	x	x	x	x	x	

\*All combinations marked with an "x" must be performed

Table 6.7.1.1: All Assessments – ASES Shoulder Score – Follow-up Visits to be compared

Evaluation Variable / Question	Level of Measurement	Analysis Plan
All Assessments – ASES Shoulder Score Comparison		

Use “ASES Total Score m [points]” and “ASES Total Score n [points]”:            Based on the underlying distribution of the data in both groups and the result of the normality assessment, either the parametric paired samples t-test or the non-parametric Wilcoxon test will be used to compare “ASES Total Score m [points]” and “ASES Total Score n [points]” to evaluate the ASES score change by subject (improvement or decrease).
 
The complete available SPSS tables content related to either the paired samples t-test or the Wilcoxon test will be included in the final report.            (Variable(s): FINSCORE)
		

Table 6.7.1.2: All Assessments – ASES Shoulder Score Comparison Tables List

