Objectives	
The objective of this clinical investigation is to demonstrate the safety and efficacy/performance of the ReUnion RSA System.
 
Efficacy/performance of the procedure will be measured the American Shoulder and Elbow Surgeons (ASES) Shoulder Score.
 
Safety of the ReUnion RSA System will be demonstrated through reporting of device-related intra-operative and post-operative Adverse Events (AEs).

Target Population	80 subjects are to be enrolled in this clinical investigation. Enrolled subjects will be assessed at Pre-Operative, Operative/Discharge, and at 6 Weeks, 6 Months, 12 Months, 24 Months and annually thereafter up to 10 years following the index procedure.

Endpoints	
Primary Endpoint:
 
The objective of the clinical investigation is to demonstrate the efficacy/performance of the device at 24 months, as measured by the ASES Shoulder Score.
 
Secondary Endpoints:
 
• Safety: Incidence of device-related intra-operative and post-operative AEs• Efficacy/Performance: Implant survivorship will be monitored
Inclusion Criteria:	
a. Subject is willing to sign the informed consent.b. Subject is willing and able to comply with post-operative scheduled clinical assessments.c. Subject is male or non-pregnant female and 18 years or older at the time of surgery.d. Subject's joint has gross rotator cuff deficiency, a functional deltoid muscle and is anatomically and structurally suited to receive the implant and subject has one or more of the following:
• Painful, disabling joint disease of the shoulder resulting from degenerative arthritis or rheumatoid arthritis• Failed previous shoulder joint replacement

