The 24 months post-operative results for subjects implanted with the ReUnion RSA System will be compared to a historical group and results reported by respective clinical outcome data in the scientific literature. The benchmark sources and values will serve as the control group for the ReUnion RSA System subjects.

Hypotheses are developed to allow for a comparison of 24 months post-operative ASES score results and 24 months effectiveness/performance between these two populations.

The Statistical Analysis Plan (SAP) lists all variables/questions within this clinical investigation. Therefore, no additional “evaluation” chapter is required nor needed for this CIP.

Data will be captured via IBM Clinical Development electronic data capture (EDC) system and statistical analysis will be performed using IBM SPSS. All statistical hypotheses tests will be with confidence levels ($1-\alpha$) of 95% and power ($1-\beta$) of 80%. The significance level (α) is 0.05 and the beta-value (β) is set to 0.20. Therefore, p -values ≤ 0.05 will indicate statistical significance.

Results will be presented using summary tables and optionally supported by graphs. For detailed information per variable, see SAP.

The primary endpoint of the clinical investigation is to demonstrate non-inferiority of the device to the selected literature controls, as measured by the ASES Shoulder Score at 24 Months post-operative. Specifically, the proposed study will test the null hypothesis that the population mean is 71.27 points. The criterion for significance (alpha) is set at 0.05. With the sample size of 10 cases, the clinical investigation will have power of 80.3% to yield a statistically significant result. This computation assumes that the population from which the sample will be drawn has a mean of 71.27 points with a standard deviation of 19.40 points. The observed value will be tested against a theoretical value (lower limit - θ) of 51.87 points. To account for an estimated appropriate overall drop-out rate, Stryker intends to enroll the calculated number of subjects, multiplied by the number of cleared indications (four) to reflect the underlying subject population adequately.

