#### 4.7. CONFIDENCE INTERVALS AND P-VALUES

The following acceptance / rejection criteria were used for this clinical investigation:

Parameter	Acceptance / rejection criteria
Confidence level (1- $\alpha$ )	0.95 (95%)
Significance level ( $\alpha$ )	0.05 (5%)
Power (1- $\beta$ )	0.80 (80%)
Beta-level ( $\beta$ )	0.20 (20%)
Confidence interval of mean	95%
p-value indicating significance	$\leq 0.05$

Table 4.7: Acceptance / Rejection Criteria

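### SAP 6.7.1 requires 78 paired ASES tests, each read at an uncorrected 0.05; if scores are stable from 24 to 120 months, the chance of at least one false change is about even (48% to 62%).

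*SAP*

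**What the plan says.** SAP 6.7.1 (ASES Comparison) states that the analysis "must compare all Total ASES Shoulder Scores of all follow-up visits against each other (m x n". Table 6.7.1.1 lists thirteen time points: pre-op, 6 weeks, 6, 12 and 24 months, then yearly to 120 months. Its footnote makes every marked combination mandatory. The yearly visits match the protocol synopsis: "and annually thereafter up to 10 years following the index procedure".

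Table 6.7.1.2 gives each pair either a paired t-test or a Wilcoxon test, chosen as follows: "Based on the underlying distribution of the data in both groups and the result of the normality assessment". The full SPSS output of whichever test is used goes into the final report.

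The threshold comes from general rules, not from 6.7.1. SAP Table 4.7 sets the "p-value indicating significance" at 0.05 or below. Protocol section 11 opens its rule with "All statistical hypotheses tests will be with confidence levels" and likewise calls p-values of 0.05 or less significant. Neither document exempts section 6.7, orders the tests, adjusts for their number or calls them exploratory.

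SAP 6.7.4 separately computes the within-subject difference for each pair of visits, with its mean, 95% confidence interval and a Shapiro-Wilk test (Table 6.7.4.2).

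**The concern.** A ten-year follow-up report will be read for whether function holds, improves or declines after the 24-month endpoint. With every visit tested against every other at 0.05, some late differences can reach significance although nothing has changed, and the plan gives no way to tell those from real ones. The tests share data, so false results also tend to cluster: one visit that is low by chance differs from several others and can look like a consistent pattern.

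The test choice is a second, smaller matter. The paired t-test assumes approximately normal differences. Normal or skewed scores at the two visits do not settle whether the differences are normal, and the plan already tests the differences in 6.7.4.

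**Working it through.** **Inputs.** From the documents: thirteen visits (SAP Table 6.7.1.1), a threshold of 0.05 (SAP 4.7, protocol section 11), 80 subjects and 56% overall drop-out (protocol 11.1, SAP 3.2). The documents give no correlation between visits, so it is assumed and varied. Section 6.7.1 states no error rate, so there is no figure of the plan's own to reproduce.

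**Count.** 13 × 12 / 2 = 78 pairs. The table as extracted carries 79 marks, one of them pre-op against itself. The sister Table 6.7.4.1 leaves that cell empty, and the stray mark is of no consequence.

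**Which pairs can give a false change.** A false positive needs two visits with truly equal means. Pre-op and early visits are expected to differ from later ones. The relevant set is therefore the nine visits from 24 to 120 months: 9 × 8 / 2 = 36 pairs.

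**Expected number.** 36 × 0.05 = 1.8, whatever the correlation.

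**Chance of at least one.**
- With equal correlation between all visits and large samples, the studentized range for nine means gives P(Q > 1.96 × √2) = 57%.
- Simulation of all 36 paired t-tests used 80 subjects, 2,000 runs per cell, no true change, and drop-out rising linearly to 56% at 120 months and unrelated to scores:

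| Assumed correlation | No drop-out | 56% drop-out |
|---|---|---|
| Exchangeable, 0.6 | 58.2% | 62.3% |
| Autoregressive, 0.5 per year | 55.9% | 58.0% |
| Autoregressive, 0.8 per year | 50.5% | 55.0% |
| Autoregressive, 0.95 per year | 48.2% | 50.7% |
| Mixture of both | 56.0% | 60.2% |

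The simulation error is about √(0.5 × 0.5 / 2000) = 1.1 percentage points. The simulated mean count was 1.72 to 1.91, in line with 1.8.

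**Clustering.** Given at least one false result, the average number is about 1.8 / 0.62 = 2.9 to 1.8 / 0.48 = 3.8.

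**If stability begins at 12 months.** 10 × 9 / 2 = 45 pairs; 45 × 0.05 = 2.25 expected; chance of at least one 53% to 70% under the same structures.

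**Test choice.** The per-test error was simulated with no true change, for normal, ceiling-limited and skewed scores, with 35 and 80 pairs and 4,000 runs each. Choosing between t-test and Wilcoxon from the raw scores gave 4.5% to 5.4%; choosing from the differences gave 4.8% to 5.1%. With a simulation error of about 0.3 points, the two cannot be told apart.

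**The case against.** The strongest reply is that nothing formal hangs on these tests. They stand under additional analyses and appear in the final report only. The primary endpoint is a single one-sample test at 24 months; the secondary endpoints are device-related adverse events and implant survivorship. No success rule refers to the pairwise results, and protocol 11.3.4 itself plans only within-subject changes. This stands and limits the point to a cheap improvement. It does not remove it: the general 0.05 rule covers these tests as written, and their output must be reported.

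A reader might also infer more than the documents support:

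- **That a false change is almost certain.** Treating the 78 tests as independent gives 1 − 0.95^78 = 98%, but they reuse the same subjects and visits. Even the simulated 63% to 83% for all thirteen visits requires no change since before surgery, which is not a realistic assumption for an arthroplasty. For 24 to 120 months the lower end falls just below one half.
- **That choosing the test from raw scores causes false changes.** The simulation shows no inflation. SAP 4.10 also makes any departure from assumptions the trigger for non-parametric methods, so the wording may need only clarification.
- **That loss of poor performers will pass for a time trend.** Each test compares the same subjects at both visits, so loss of low scorers does not in itself create a within-pair change; bias needs drop-out related to the course of the scores. With no true change and drop-out made likelier after a low previous score (assumed log-odds slope 0.5 to 1 per SD), the mean 24-to-120-month difference in completers moved only about −0.3 to −0.7 points, and the chance of a false change was 61% to 70%. The documents do not say how drop-out relates to scores. SAP 4.6 and Table 6.7.4.2 do report the numbers missing, so shrinking subsets would be visible.

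**Conclusion.** The point holds as one of uncorrected multiplicity in an additional analysis. As written, the plan requires 78 distinct tests at 0.05 each. If scores are stable from 24 to 120 months, about 1.8 of 36 late comparisons will be falsely significant on average, and the chance of at least one is about 48% to 62%. The expected count needs only equal true means and a 5% error per test. The probability rests on assumed correlations (the upper end from exchangeable 0.6, the lower from autoregressive 0.95 per year) and on drop-out that is absent or random up to 56%. It is the chance of any false result in the set, not of a particular one.

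Basing the test choice on the two visits' scores is a separate, minor method error without measurable effect on false positives. The primary and secondary conclusions stand untouched.

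**What to change.** Amend SAP 6.7.1 in three places:

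1. Name a small set of contrasts in advance, for example 24 months against pre-op and 120 against 24 months, and test them with Holm correction. With two contrasts, the smaller p-value is compared with 0.05 / 2 = 0.025 and, if that is met, the larger with 0.05. Correcting all 78 instead would mean a Bonferroni threshold of 0.05 / 78 = 0.00064, which serves little purpose here.
2. Report all other pairwise differences through 6.7.4 as estimates with 95% confidence intervals, with a sentence that they are descriptive and not read against 0.05.
3. Base the choice between paired t-test and Wilcoxon test on the Shapiro-Wilk result for the differences, which Table 6.7.4.2 already produces.

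A mixed model on all visits is an optional sensitivity analysis for drop-out, since it uses subjects with partial records. If adopted, it has to be squared with SAP 4.10, which sends non-normal data to non-parametric methods.

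The cost is SAP wording and fewer p-values in the final report. No new data are needed.
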